### 4.5.3 Additional Safety Assessments

#### Safety laboratory assessments

Safety laboratory assessments (biochemistry, haematology, glucose metabolism, hormones, antibodies and lipids) will be summarised by treatment and time of assessment. All abnormal values will be listed.

#### Vital signs and Electrocardiograms

Vital signs (pulse rate, systolic and diastolic blood pressure) will be summarised by treatment and time of assessment. The investigator’s evaluation of ECG classifications will be tabulated by treatment and time of assessment.

#### Antibodies

For participants randomised to somapacitan with confirmed anti-somapacitan antibody positive samples, the anti-somapacitan positive cross-reactivity to hGH antibodies and in vitro neutralising

effect will be tabulated by time of assessment.

## 4.6 Other Analyses

The subsections refer to analysis of other parameters. For calculation of other parameters please see appendix 1, section [6.1](#).

### 4.6.1 PRO analysis

The following Patient reported outcome questionnaires would be collected in the trial:

- GHD-CIM (Growth Hormone Deficiency – Child Impact Measure)
- GHD-CTB (Growth Hormone Deficiency – Child Treatment Burden)
- GHD-PTB (Growth Hormone Deficiency – Parent Treatment Burden)

The PRO data will be analysed based on the ‘on –treatment’ observation period only.

Title	Time frame	Unit
Change in GHD-CIM (domain and total scores)	From Baseline (Week 0) to visit 5 (Week 26), Baseline (Week 0) to Week 52	-100 to 100
GHD – CTB (domain and total scores)	At visit 5 (Week 26) At visit 7(Week 52)	0 to 100
GHD – PTB (domain and total scores)	At visit 5 (Week 26) At visit 7(Week 52)	0 to 100

GHD – CTB scores and GHD – PTB scores will be analysed using an MMRM with an unstructured covariance matrix on all relevant post-baseline values as dependant variables. The model will include treatment, sex, age group, GH peak group and sex by age group interaction term as factors, all nested within week as a factor. From the MMRM, the treatment differences will be estimated and the corresponding 95% CI and p-values will be reported for week 26 and week 52, respectively.

Changes from baseline to week 26 and week 52 in GHD-CIM scores will be analysed using an MMRM with an unstructured covariance matrix. The model will include treatment, sex, age group, GH peak group and sex by age group interaction term as factors and baseline value as a covariate, all nested within week as a factor. From the MMRM, the treatment differences will be estimated and the corresponding 95% CI and p-values will be reported for week 26 and week 52, respectively.

In addition, the following questions of the physical domain of the GHD-CTB PRO will be analysed using Wilcoxon rank sum tests:

- In the past week, how much did your child's injections hurt
- In the past week, how much did your child's injections sting
- In the past week, how much bruising did your child have from their injections
- In the past week, how much soreness did your child have at their injection site

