### 1.2 Study Design

A randomised open-labelled two arm phase 3 trial designed to confirm non-inferiority of efficacy and investigate safety of once weekly subcutaneous treatment of somapacitan compared to daily subcutaneous growth hormone (Norditropin®) treatment in Chinese prepubertal children with growth hormone deficiency.

[figure not shown]
The total trial duration for a subject will be up to 70 weeks approximately.

The trial duration includes a 2 to 14 weeks of screening period, a 52 weeks of treatment period and a minimum 30 days of follow up period.

Eligible subjects will be randomised in a 2:1 manner to receive either somapacitan or Norditropin®

The non-inferiority margin of -2.0 cm/year is used in the trial. The randomisation will be stratified by age (<6 versus  $\geq 6$  years), gender (boys versus girls) and GH peak (< 7 versus  $\geq 7$  ng/ml) to minimize bias on the primary endpoint.

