### Figure 1 Study design

## 2 Statistical Hypothesis

Hypothesis testing for the primary endpoint will be done by testing  $H_0: D \leq -2 \text{ cm/year}$  vs  $H_A: D > -2 \text{ cm/year}$ , where  $D$  is the mean treatment difference (smapacitan – Norditropin®). Non-inferiority of somapacitan will be considered confirmed if the lower boundary of the two-sided 95% confidence interval is above -2 cm/year. As only one confirmatory hypothesis is to be tested, no further control for multiplicity is needed.

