## 4 Statistical Analyses

### 4.1 General Considerations

The one-sided test used for the primary endpoint is based on an alpha level of 2.5%. All other statistical tests conducted will be two-sided on the 5% significance level.

Two factors are defined as follows:

- Age group: Age at randomisation (<6 versus  $\geq 6$  years)
- GH peak group: Growth hormone peak level (< 7 versus  $\geq 7$  ng/ml)

All efficacy endpoints will be analysed using FAS and all safety endpoints will be analysed using SAS.

The primary endpoint will additionally be analysed using PP as a support to the results achieved using FAS under the hypothetical strategy.

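### The four GHD-CTB injection items use an unstratified Wilcoxon test although randomisation is stratified by age, sex and GH peak; stratifying by age group is a near-free improvement of low impact

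*SAP*

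**What the plan says.** SAP 4.6.1 lists four single questions from the GHD-CTB physical domain (how much the injections hurt and stung, how much bruising, how much soreness) and says that they "will be analysed using Wilcoxon rank sum tests". Protocol 9.4.5 plans the same test. Neither names strata, covariates or a time point for it.

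SAP 1.2 sets out the allocation: "The randomisation will be stratified by age (<6 versus" 6 years and above), "gender (boys versus girls) and GH peak (< 7 versus" 7 ng/ml and above), at 2:1. That makes 2 x 2 x 2 = 8 cells.

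For the GHD-CTB and GHD-PTB scores, SAP 4.6.1 uses an MMRM: "The model will include treatment, sex, age group, GH peak group and sex by age group interaction term as factors". The domain that contains the four items is therefore adjusted, while the items are not.

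On error control, SAP 4.1 says "All other statistical tests conducted will be two-sided on the 5% significance level", and SAP section 2 says "As only one confirmatory hypothesis is to be tested, no further control for multiplicity is needed". The item tests lie outside that one confirmatory hypothesis.

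**The concern.** When allocation is balanced within strata, differences in outcome between strata cannot add to the chance difference between arms. The ordinary Wilcoxon variance still counts them. If the strata predict the answers, that variance is too large, the test rejects too rarely under the null, and it loses power.

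Age is the natural candidate: Protocol 5.1 admits children from 2 years and 26 weeks up to 10 (girls) or 11 (boys) years, and reported injection discomfort could well differ between younger and older children. At stake is the ability to see a difference in injection discomfort, in either direction, between a weekly and a daily product. Protocol 2.2.2 gives a lower treatment burden as an aim of weekly dosing. The plan also gives no reason for adjusting the domain score but not its items.

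**Working it through.** **1. The plan's own figures.** The documents give no power or type I error for the item tests. Their only power table is for the primary endpoint, and it confirms the inputs borrowed here (108 children, 2:1, 10% loss). With 10% removed, the arms are 64.8 and 32.4. At SD 2.6 the standard error is 2.6 x sqrt(1/64.8 + 1/32.4) = 0.559, the noncentrality is 2/0.559 = 3.58, and one-sided 2.5% t-test power is 94.3% (stated: 94%). At SD 2.5, 2.7 and 2.8 it is 95.7%, 92.6% and 90.8% (stated: 95%, 92%, 90%).

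**2. Mechanism.** The plain test uses Var(W) = (n1 n0 / n) x s², where s² is the variance of all ranks. If strata explain a share R² of the rank variance and arms are balanced within strata, the true variance is about (1 - R²) times that. Type I error is then about 2Φ(-1.96/sqrt(1 - R²)):
- R² = 0: 5.0%
- R² = 0.10: 2Φ(-2.066) = 3.9%
- R² = 0.20: 2Φ(-2.191) = 2.8%
- R² = 0.30: 2Φ(-2.343) = 1.9%

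This is the limit with perfect balance. Incomplete blocks, missing answers and coarse items weaken it, so simulation is needed.

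**3. Simulation with age as the predictor.** All effects are assumed, the item has 5 levels, and tests are two-sided at 5%.
- Run A: 72 versus 36 children, eight equal strata, none missing, treatment log-odds -0.8, 4,000 runs.
- Run B: 108 children, uneven strata, permuted blocks of 6, 10% missing, treatment log-odds -1.0, 6,000 runs.

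Entries are plain Wilcoxon / van Elteren by age / van Elteren over eight cells, in %.

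| Run | Age log-odds | Power | Type I error |
|---|---|---|---|
| A | 0 | 56.4 / 56.3 / 55.5 | 5.0 / 5.2 / 5.3 |
| A | -1.0 | 48.7 / 51.5 / 50.8 | 4.4 / 5.4 / 5.6 |
| A | -1.5 | 43.7 / 49.7 / 48.9 | 3.4 / 4.8 / 5.1 |
| B | 0 | 64.6 / 64.5 / 63.7 | 5.1 / 5.1 / 5.3 |
| B | -0.5 | 63.3 / 63.7 / 62.0 | 4.9 / 5.0 / 5.0 |
| B | -1.0 | 60.4 / 62.5 / 61.1 | 4.6 / 5.2 / 5.0 |
| B | -1.5 | 55.0 / 61.1 / 59.7 | 4.2 / 5.3 / 5.5 |

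Monte Carlo standard errors are about 0.6 to 0.8 points for power and 0.3 to 0.35 for type I error. The gain from age stratification is 51.5 - 48.7 = 2.8 and 62.5 - 60.4 = 2.1 points at -1.0, and 49.7 - 43.7 = 6.0 and 61.1 - 55.0 = 6.1 points at -1.5. With no age effect the difference is -0.1 in both runs.

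**4. Simulation with all three factors as predictors.** Here R² is the share of latent item variance explained by the strata. Assumed: stratum proportions 0.4, 0.7 and 0.6, blocks of 6, 10% missing, 5-level item with half the answers in the lowest level, latent shift 0.6 SD; 6,000 runs for type I error and 4,000 for power. Entries are plain / van Elteren over eight cells / rank ANCOVA with the MMRM factors, in %.

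| R² | Power | Type I error |
|---|---|---|
| 0 | 65.3 / 63.0 / 64.8 | 4.7 / 4.5 / 4.7 |
| 0.05 | 65.0 / 65.7 / 66.3 | 5.3 / 5.8 / 5.7 |
| 0.10 | 65.6 / 66.1 / 67.6 | 4.3 / 4.9 / 5.0 |
| 0.20 | 64.9 / 69.5 / 70.0 | 3.6 / 4.8 / 4.9 |
| 0.30 | 65.5 / 74.2 / 73.6 | 2.4 / 4.7 / 4.9 |

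The cost of eight cells when nothing is prognostic is 65.3 - 63.0 = 2.3 points here and 0.9 points in runs A and B. The reason is cell size: 108/8 = 13.5 children per cell on average, of whom about 4.5 are controls.

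**The case against.** A reader might infer that stratified randomisation by itself makes the plain test conservative and costs power. The documents do not support that. The effect needs strata that predict the answers, and nothing in the protocol or SAP says that age, sex or GH peak predicts hurt, sting, bruising or soreness. The questions are worded to a carer, so an age effect through the child's own reporting cannot be presumed. Log-odds of -1.0 and -1.5 are odds ratios of about 2.7 and 4.5 between age groups, which is a strong effect. At R² of 0.05 to 0.10 the adjusted tests gain only about 0 to 2 points.

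It is also fair that the planned test showed no excess type I error, that a simple rank test is a legitimate supplement for single ordinal items, and that the adjusted physical-domain score and the adverse-event collection of injection site reactions also address discomfort. The items are therefore not the trial's only comparison of injection discomfort. Because the protocol itself names the Wilcoxon test, changing it is a departure from the protocol that has to be declared.

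All of this stands, and it limits the point to a low-impact improvement. It does not show a drawback to stratifying by age group alone, which cost nothing measurable when age had no effect. The objection that stratifying can lose power applies to the eight-cell version.

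**Conclusion.** The planned item tests are valid but leave out a grouping that the trial already randomises by and that the same section adjusts for elsewhere. If age group is clearly prognostic, they are mildly conservative and lose about 2 to 6 points of power under assumed age log-odds of -1.0 to -1.5. If it is not, there is essentially no difference. The sizes rest on assumed item distributions, treatment effects, stratum proportions, block size and missingness, none of which the documents give for these items (the 10% loss is borrowed from the primary endpoint).

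The impact is low. The items sit under other analyses, outside the confirmatory hypothesis; the primary conclusion and the adjusted GHD-CTB scores are unaffected.

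**What to change.** In SAP 4.6.1 and Protocol 9.4.5, replace the plain test for the four items with the van Elteren (stratified Wilcoxon) test, stratified by age group (<6 versus ≥6 years). A rank ANCOVA with sex, age group, GH peak group and sex by age group is an acceptable alternative that matches the MMRM; it lost 0.5 points at most (65.3% versus 64.8%) when the strata were not prognostic. Do not stratify by all eight cells.

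SAP 4.8 currently declares no changes from the protocol, so it should list this one. SAP section 1 says that version 1.0 preceded unblinding but does not say so for version 2.0. If the data are already unblinded, keep the plain Wilcoxon as planned and add the stratified test as a labelled sensitivity analysis.

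The cost is a sentence in each document, the entry in SAP 4.8 and one option in the analysis program. No further data are needed.

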#### **4.6.2 Pharmacokinetic and/or pharmacodynamic modelling**

Somapacitan and IGF-I serum concentration data may be used for population PK, population PK/PD and exposure-response modelling, potentially as a joint analysis of data from multiple trials. Other exploratory PK/PD and exposure-response analyses for this trial may be performed if deemed relevant. If conducted, a more technical and detailed elaboration of the population PK, population PK/PD and exposure-response analyses will be given in a prospective modelling analysis plan.

#### **4.6.3 Subgroup Analysis**

Not applicable

#### **4.7 Interim Analysis**

Not applicable

#### **4.8 Changes to Protocol-planned Analysis**

There are no changes to the protocol-planned analysis.

## 5 Sample size determination

Approximately 108 subjects will be randomly assigned to trial product.

The sample size calculation is based on the primary estimand. It is expected based on phase 2 trial data (NN8640-4172) that the proportion of subjects with no landmark visit data or who discontinued randomised treatment before landmark visit is 10% with similar withdrawal reasons in the two treatment arms. NN8640-4172 is a global trial, including Japanese subjects, and therefore trial information from 4172 is expected to also be of use when planning for a somapacitan phase 3 trial in China. It is expected that subjects discontinuing their randomised treatment will start on ancillary treatment, if no medical reasons prohibit this. Thus, data assessed after discontinuation of the randomised treatment will not be used for the primary analysis of the primary endpoint based on the primary estimand. Assuming the same proportions of subjects with no landmark visit and subjects discontinuing randomised treatment but have landmark visit data in the two arms leads to the following sample size calculation.

The sample size is determined using a non-inferiority margin of -2.0 cm/year and a one sided two-group t-test with a significance level of 2.5% for a 2:1 randomisation ratio between somapacitan and Norditropin®.

Based on data from NN8640-4172, a standard deviation for HV at week 52 was chosen (SD=2.6 cm/year) for the sample size calculation giving a sample size of 108 subjects. Different SD scenarios with power calculation for the primary analysis are presented in the table below under the assumption of a true difference in annualized HV of 0 cm/year between the two treatment arms.

Table 9 Calculated power with 108 subjects randomised 2:1

SD	2.5 cm/year	2.6 cm/year	2.7 cm/year	2.8 cm/year
	95%	94%	92%	90%

The SD candidates are based on reported SD values from clinical trials: Valtropin phase 3 trial, 52 weeks (SD=2.8, 3.0), OPKO phase 2 trial, 52 weeks (SD=2.1, 2.3, 2.6, 3.5), and NN8640-4172,

phase 2 trial, 52 weeks (SD=2.3, 2.6).

For sensitivity analysis, a one-way tipping point analysis is planned. Based on a penalty of 2 cm/year for subjects in the somapacitan arm who have missing landmark visit data or discontinue randomised treatment before landmark visit, this gives a power of ~92% (adjusted treatment effect  $0.9*0 - 0.1*2 = -0.2$ ).

If the per protocol analysis set (PP) is assumed to consist of ~85% of the trial subjects (same proportion across treatment groups), giving 60 subjects in the somapacitan arm and 30 subjects in the Norditropin® arm, then repeating the primary analysis based on the primary estimand on the PP should result in a power of 92% for confirming non-inferiority of somapacitan compared to Norditropin®, under the assumption of no true treatment difference between the two treatments.

## 6 Supporting Documentation

### 6.1 Appendix 1: Definition and calculation of endpoints, assessments and derivations

Type	Title	Time frame	Unit	Details
Primary endpoint	Height velocity	Height velocity (annualised) at week 52	cm / year	HV = (height at 52 weeks visit - height at baseline)/(time from baseline to 52 weeks visit in years). Annualized HV at the intermediate visits: Week 13, 26 and 39, will be derived analogously to the week 52 HV: HV = (height at j weeks visit - height at baseline)/(time from baseline to j weeks visit in years), j=13, 26, 39.
Supportive secondary efficacy endpoint	Change in bone age	From visit 1 to week 52	Years	
Supportive secondary efficacy endpoint	Change in Height Standard Deviation Score	From baseline (week 0) to week 52	-10 to +10	Height SDS will be derived using Chinese general population standards and HV SDS will be derived using Prader standards  as reference data
Supportive secondary efficacy endpoint	Change in Height Velocity Standard Deviation Score	From baseline (week 0) to week 52	-10 to +10	
Supportive secondary safety endpoint	Change in fasting plasma glucose	From baseline (week 0) to week 52	mmol/l	

Type	Title	Time frame	Unit	Details
Supportive secondary safety endpoint	Change in HbA1c	From baseline (week 0) to week 52	%	
Supportive secondary endpoint	Change in IGF-I Standard Deviation Score	From baseline (week 0) to week 52	-10 to +10	
Supportive secondary endpoint	Change in IGFBP-3 Standard Deviation Score	From baseline (week 0) to week 52	-10 to +10	
Patient reported outcomes	Change in GHD-CIM (domain and total scores)	From Baseline (Week 0) to visit 5 (Week 26), Baseline (Week 0) to Week 52	-100 to 100	
Patient reported outcomes	GHD – CTB (domain and total scores)	At visit 5 (Week 26) At visit 7(Week 52)	0 to 100	
Patient reported outcomes	GHD – PTB (domain and total scores)	At visit 5 (Week 26) At visit 7(Week 52)	0 to 100	

